2.1.2 Part B

Part B of the study will last for 18 months (from V1B to V22B). The scheme of visits will mirror the Part A scheme. The first visit of Part B (V1B) will take place at least 18 months after the patient started Part A (i.e., patient should have completed V23 which is month 18 of Part A to enter Part B). The study scheme for Part B is shown in also included in Figure 2.

The patients randomized to the placebo group during Part A will receive five monthly (every four weeks) immunizations with ABvac40 plus a booster shot after 6 months (Placebo arm Part A / ABvac40 arm Part B), whereas the patients randomized to the ABvac40 group during Part A will receive placebo following this schedule, except in V13B (Week 16), where they will receive an ABvac40 booster shot (ABvac40 arm Part A / Placebo+Booster arm Part B). Given the extended inclusion period of Part A, the V13B booster will take place at different timepoints relative to the patients' last immunization.

Figure 2: AB1601 Study Schematic – Part B

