2.3 Study Population

Patients (between 55-80 years of age) diagnosed either with a-MCI or vm-AD will be included in the trial. To ensure sufficient precision for the primary safety and efficacy endpoints of the study a minimum of 60 patients with a-MCI or vm-AD per treatment group (ABvac40 and placebo) are required. The amyloid Positron Emission Tomography (a-PET) positive and a-PET negative patients will be independently randomized following a 1:1 ratio between ABvac40 and placebo (Part A).

Participants in Part A will have to complete at least their 18-month visit (V23) to be eligible for Part B of the study.

All patients who have participated in Part A who have not experienced any drug reaction and have no Magnetic Resonance Imaging (MRI) safety findings before the first immunization in Part B, may participate in Part B. On completion of Part A of the study, the database containing Part A data will undergo DBL prior to reporting of Part A results. Additionally, Part A and B data will undergo DBL prior to reporting of Part B results.

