3 GENERAL STATISTICAL CONSIDERATIONS AND REPORTING CONVENTIONS

The following general analysis and reporting conventions will be used:

- The following treatment labels will be used for presentation of results in the statistical tables:
 - Statistical testing of primary and secondary efficacy outcomes in Part A of the study and summaries of Adverse Events (AE)s across parts A and B of the study will be presented by the following treatment groups:
 - ABvac40
 - Placebo
 - Summary statistics for all other parameters (Part A and Part B, combined) will be presented by the following treatment sequences:
 - ABvac40 arm Part A / Placebo+Booster arm Part B
 - Placebo arm Part A / ABvac40 arm Part B
- Visits will be presented in outputs in terms of weeks, with a suffix of “A” or “B” to indicate the study part (e.g. Week 0A, Week 2A..... Week 0B, Week 2B, etc...).
- Only available data will be included in summary statistics and no substitutions or imputations of missing values will be performed.
- Categorical variables will be summarized using counts (n) and percentages (%) and will be presented in the form n (%). Percentages will not be presented for counts of 0, while percentages of 100 will be reported as a whole number (i.e. “100%”). All other percentages will be presented to 1 decimal place. To ensure completeness, summaries for categorical variables will include all categories, even if no patients had a response in a particular category. Denominators will include patients with non-missing data, unless otherwise specified. The number of patients with missing data for categorical variables will be summarized without a percentage.
- Continuous variables will be summarized using mean, 95% confidence interval (CI) for mean, standard deviation (SD), first quartile (Q1), third quartile (Q3), minimum, maximum, median, and number of patients. The mean, median, Q1, Q3 and CI will be rounded and reported to 1 more level of precision than the original observations, and the SD will be rounded and reported to 2 more levels of precision than the original observations. The minimum and maximum will be reported to the same precision as the original data.
- Following SAS default rules, the median will be reported as the rounded average of the two middle sorted values if the dataset contains even numbers of non-missing data.

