7.2 Summary of Primary Safety Outcome

7.2.1 Adverse Events

Adverse events will be classified as Treatment-Emergent AEs (TEAEs) or non-Treatment-Emergent AEs (non-TEAEs), based on the comparison of the AE onset date/time with the start date/time of study treatment.

- A TEAE will be defined as an AE which starts or worsens in severity during or after the first administration of study treatment.
- A non-TEAE will be defined as an AE which starts or worsens in severity prior to the start of the first administration of study treatment.

The following algorithm will be used to identify the treatment group under which each AE will be summarized:

For SAESIs:

- AEs that start or worsen in severity at any time after a patient's first dose of ABvac40 will be associated with the ABvac40 treatment group.
- AEs that start or worsen in severity after first dose of Placebo, but before first dose of ABvac40, will be associated with the Placebo treatment group

For non-SAESIs:

- For patients randomised to the ABvac40 arm Part A / Placebo+Booster arm Part B treatment sequence:
 - AEs that start or worsen in severity at any time during or after a patient's first dose of study drug in part A and prior to their booster ABvac40 vaccination will be associated with the treatment received at their last injection prior to the AE.
 - AEs that start or worsen in severity during or after a patient's booster ABvac40 vaccination will be associated with the ABvac40 treatment group.
- For patients randomised to the Placebo arm Part A / ABvac40 arm Part B treatment sequence:
 - AEs will be associated with the treatment received at their last injection prior to the AE.

For the purposes of classifying AEs as treatment emergent and to assign treatment groups, partial AE start and end dates will be imputed to allow comparison with the study treatment date start and end dates. Section 9.1.1 below presents the imputation rules. Note, the imputed dates will be used for classification purposes and treatment group assignment purposes only and the original partial AE dates will be presented in data listings.

An overall summary of AEs will be presented by treatment group, by providing counts and percentages of patients with any: TEAE, non-TEAE, Treatment related TEAEs, TEAE leading to treatment discontinuation, TEAEs leading to death, Treatment-Emergent Serious AE (TESAE), Treatment-

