Emergent SAESIs, Treatment related TESAEs, TESAEs leading to treatment discontinuation and TESAEs leading to death.

Counts and percentages of patients will be presented by treatment group, SOC and PT for the following: TEAEs, non-TEAEs, TEAEs leading to study withdrawal, Treatment-Emergent SAESIs and TESAEs.

Counts and percentages of patients with TEAEs will be presented by treatment group, SOC, PT and maximum causality.

Counts and percentages of patients with TEAEs will be presented by treatment group, SOC, PT and maximum severity.

For summaries by maximum causality/severity, if a patient reported more than one AE with the same PT, the AE with the maximum causality/severity will be presented. If the causality/severity of an AE is missing, the causality/severity will be treated as missing in summaries. If a patient reported more than one AE within the same SOC, the patient will be counted only once under the maximum causality/severity within the SOC.

The denominator for the percentages for the ABvac40 group will be all patients in both the ABvac40 arm Part A / Placebo+Booster arm Part B and Placebo arm Part A / ABvac40 arm Part B treatment sequences who took at least one dose of ABvac40 throughout the study.

The denominator for the percentages for the Placebo group will be all patients in both the ABvac40 group Part A / Booster group Part B and the Placebo arm Part A / ABvac40 arm Part B treatment sequence who took at least one dose of Placebo.

In Part B, the safety population will be those subjects who received at least one dose.

AEs will be listed by treatment group and patient identifier. In addition, patients with SAEs and AEs leading to premature discontinuation of treatment period from the study will be individually listed.

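### SAP 7.2.1: in the pooled Part A+B tables, the placebo percentage for serious AEs of special interest is divided by patients who cannot contribute such an event

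*SAP*

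**What the plan says.** SAP section 3 states that "summaries of Adverse Events (AE)s across parts A and B of the study will be presented by the following treatment groups", namely ABvac40 and Placebo. SAP 7.2.1 then sets out how events and patients are allotted to those two columns.

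- **SAESI numerator, ABvac40.** An event that starts or worsens at any time after the patient's "first dose of ABvac40 will be associated with the ABvac40 treatment group".
- **SAESI numerator, placebo.** An event that starts or worsens "after first dose of Placebo, but before first dose of ABvac40, will be associated with the Placebo treatment group".
- **Other AEs, ABvac40-first sequence.** Events from the first Part A dose and "prior to their booster ABvac40 vaccination will be associated with the treatment received at their last injection prior to the AE". From the Part B booster on, they go to ABvac40.
- **Placebo denominator.** "The denominator for the percentages for the Placebo group will be all patients in both the ABvac40 group Part A", together with the placebo-first sequence, provided the patient took at least one placebo dose. SAESIs have no separate rule.

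SAESI percentages are called for twice in 7.2.1: in the overall AE summary, and by SOC and PT. Under SAP 2.1.2, ABvac40-first patients receive placebo in Part B at every vaccination visit except V13B (week 16), when they receive the ABvac40 booster.

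**The concern.** The numerator and the denominator of one percentage follow different rules. An ABvac40-first patient has already had ABvac40 when the first placebo injection is given in Part B. Every later SAESI in that patient therefore belongs to ABvac40, yet the patient still counts in full in the placebo denominator. The ABvac40 column has no such mismatch, because everyone in its denominator can contribute an ABvac40 event.

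ARIA is the main imaging safety event in this programme. Placebo cases are plausible: protocol 2.2 reports that the only micro-haemorrhage seen on MRI in Phase I was in a placebo patient. Protocol 9.1.3.1 judges safety on the overall pattern of AEs, so readers will compare these two percentages directly.

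A second, lesser matter is that the pooled tables give crude patient percentages although time at risk differs between the columns.

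**Working it through.** **Inputs**

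- 60 patients per arm (SAP 3.2). This reproduces: the rule of three gives 3/0.05 = 60, and 1 − 0.95^60 = 0.954, above the stated 95%.
- About 35 completers per arm, which protocol 9.2 gives as an expected minimum.
- r, the number of ABvac40-first patients given placebo in Part B. The documents do not state it. Entry requires V23 and passing a safety screen (SAP 2.3), so r could lie on either side of 35. I show 20, 35 and 60; 60 is the limit at which everyone continues.

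**SAESI denominator**

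Patients who can supply a placebo SAESI: 60. Denominator under the SAP rule: 60 + r. Factor: 60/(60+r).

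| r | Denominator | Factor | Three events print as | Three events among those at risk |
|---|---|---|---|---|
| 20 | 80 | 0.75 | 3/80 = 3.8% | 3/60 = 5.0% |
| 35 | 95 | 0.63 | 3/95 = 3.2% | 5.0% |
| 60 | 120 | 0.50 | 3/120 = 2.5% | 5.0% |

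In a Part A-only table no ABvac40-first patient has yet had placebo, so the same rule gives 60 and a factor of 1.

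**Time at risk, AEs other than SAESIs**

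Assume r = 35 in each arm, 77 weeks of Part A for all 60, 77 weeks of Part B, and no gap between the parts. An ABvac40-first patient then has 16 placebo weeks in Part B (V1B to V13B) and 77 − 16 = 61 ABvac40 weeks.

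- Placebo: 60×77 + 35×16 = 5,180 patient-weeks; 5,180/95 = 54.5 per patient in the denominator.
- ABvac40: 60×77 + 35×61 + 35×77 = 9,450 patient-weeks; 9,450/95 = 99.5 per patient.
- Ratio: 9,450/5,180 = 1.82.

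What this does to the crude percentages depends on the model. The figures below also use r = 35, and the model inputs are assumptions.

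- *No drug effect, constant hazard* (Part A taken as 21 months, dropouts leaving uniformly): the ABvac40/placebo ratio is 1.80 at 10% annual risk and 1.35 at 75%.
- *No drug effect, equal risk per injection* (1% to 30%): 1.08 to 1.32.
- *Vaccine effect that persists from the first ABvac40 dose*: take f(n) = 1 − (1−q)^n, q = 0.05 without vaccine, and 25 dropouts per arm with 4.5 doses each. With risk doubled to 0.10:
  - ABvac40 = [35 f(8) + 25 f(4.5) + 35 f(6)]/95 = (35×0.570 + 25×0.378 + 35×0.469)/95 = 48.2%.
  - Placebo = [35 f(6) + 25 f(4.5)] at q = 0.05, plus 35 f(4) at q = 0.10, all over 95 = (35×0.265 + 25×0.206 + 35×0.344)/95 = 27.9%.
  - The pooled ratio is 1.73. Part A alone gives (35×0.469 + 25×0.378)/(35×0.265 + 25×0.206) = 1.79.
  - At 1.5 times the risk the pair is 1.54 pooled against 1.42 in Part A. At 3 times it is 1.93 against 2.41.

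The pooled crude ratio can therefore lie above or below the randomised Part A ratio.

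**The case against.** The strongest reply is that little hangs on this. The tables are descriptive, counts are printed beside percentages, and a reader can recompute. Part A is also locked and reported separately ("the database containing Part A data will undergo DBL prior to reporting of Part A results"), and there the rule gives the right denominator. All of that stands and limits the scope to the pooled tables. It does not make the pooled percentage right, and the SAP text itself fixes the denominator.

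A reader might infer that the fault hides a vaccine signal. It does the reverse: it lowers only the placebo percentage. Nor can one conclude that the ABvac40 percentage is too high overall, since that column gains delayed-start patients "who have not experienced any drug reaction and have no Magnetic Resonance Imaging (MRI) safety findings before the first immunization in Part B", which could lower it.

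A reader might also infer that pooling as such biases every AE comparison against ABvac40. The calculations do not support a fixed direction. Unequal exposure is plain from the design, and exposure-adjusted rates are an improvement rather than the correction of an error.

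Finally, one might infer that the SAP has dropped the Part A AE comparison, the combined cardiac and vascular group, and the exploratory Fisher's test. SAP 7.2.1 does not restate them. But SAP 1.1 describes the SAP as supplementing the protocol and keeps table specifications in separate documents, so protocol 9.1.3.1 still governs. That is missing detail, not a removal.

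**Conclusion.** The SAESI rule is wrong as written for the pooled Part A+B tables. The placebo percentage is too low by the factor 60/(60+r) whenever a placebo SAESI occurs and r is above zero: 0.63 at r = 35, and 0.75 to 0.50 over r = 20 to 60. This assumes 60 treated patients per arm, dosed as randomised; a misallocated patient given placebo before any ABvac40 could contribute a placebo SAESI. The size depends on r, but the direction for the placebo percentage does not. No confirmatory test is affected. Unequal time at risk is a real but secondary matter, with a net effect that depends on the model. It should be corrected because it concerns the main event of special interest and costs almost nothing to put right.

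**What to change.** 1. Add one sentence to SAP 7.2.1: for SAESIs, the placebo denominator is the patients who received placebo before any dose of ABvac40. Apply it to the SAESI row of the overall summary and to the SAESI table by SOC and PT.
2. SAESI terms such as ARIA also appear in the pooled TEAE and TESAE tables. Use the same denominator for those terms there, or footnote the difference. Otherwise one term would carry two unexplained placebo percentages (5.0% and 3.2% for three events at r = 35).
3. As an addition, show exposure-adjusted rates beside the pooled A+B counts, with time at risk allotted by the same rules as the events.

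The cost is SAP wording, a few re-programmed tables and a footnote. No new data are needed.

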7.3 Summary of Secondary Safety Outcomes

7.3.1 Withdrawal Criteria (Study Continuation Decision)

Summary of withdrawal criteria and study continuation decision will be presented as part of the summary of disposition, see section 5.1 above.

7.3.2 Physical Examination

Physical examination results will be summarized in the form of a shift table, presenting the shift in results (Normal, Abnormal non-clinically significant, Abnormal clinically significant, Not done) from baseline to each post-baseline visit, by treatment sequence group for Part A and Part B.

A listing of physical abnormalities will also be presented.

7.3.3 Neurological Examination

Neurological examination results will be summarized in the form of a shift table, presenting the shift in results (Normal, Abnormal non-clinically significant, Abnormal clinically significant, Not done) from baseline to each post-baseline visit, by treatment sequence group for Part A and Part B.

A listing of neurological abnormalities will also be presented.

7.3.4 Prior and Concomitant Medications

Prior and concomitant medications will be summarized separately, by treatment sequence, medication class (ATC level 2) and medication sub-class (ATC level 4). Summaries of concomitant medications will be presented for Part A only, Part B only and separately for parts A and B combined.

Medications will be sorted alphabetically by ATC level 2 and ATC level 4. If the ATC level 4 term is missing, the ATC level 3 term will be used in the medication summary table and data listing.

Appendix 9.1.2 outlines the conventions that will be used to impute missing or partial medication start/end date information in order to determine whether a medication is prior or concomitant.

A listing of prior and concomitant medications will also be presented. Medication start/end dates will be presented as recorded in the electronic Case Report Form.

7.3.5 Vital Signs

Vital signs parameters will be summarized by timepoint within each scheduled visit and treatment sequence group for Part A and Part B. The summaries will include change from baseline to each timepoint within each scheduled post-baseline visit. A listing of vital signs results will also be presented.

7.3.6 Electrocardiogram

ECG parameters HR, PR interval, QRS and QT will be summarized by study visit and treatment sequence group for Part A and Part B.

Each of the ECG parameters were classified as normal or abnormal at each visit. Using this information, the overall ECG finding at each visit will be categorized as:

- Abnormal – if any one of the individual ECG parameters are abnormal at that visit
- Normal – if all the individual ECG parameters are normal at that visit
- Missing – if at least one of the individual ECG parameters is missing and none of the non-missing ECG parameters are abnormal.

These categorizations of ECG findings will be summarized using a shift table, presenting the count and percentage of patients whose categorizations change or remain the same from baseline to each post-baseline scheduled visit. The shift table will be presented by treatment sequence and will include “Missing” as a result category

A listing of ECG findings and results will also be presented.

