4.1 Endpoints

4.1.1 Part A

The primary endpoint for safety is the incidence of AEs (overall or grouped as neurological, psychiatric or cardiovascular).

The hypothesis for the primary endpoint for safety is that ABvac40 will be safe for human administration, according to the observed pattern of AEs. The trial will be considered satisfactory if the pattern of AEs (overall or grouped as neurological, psychiatric or cardiovascular) is consistent with a good safety and tolerability profile of ABvac40 for human administration at the final visit.

Additionally, the following secondary safety endpoints will be evaluated including:

- number of withdrawn patients due to adverse events (AEs)
- number of withdrawn patients due to other causes
- number of serious adverse events (SAEs)
- number of clinically significant changes in physical and neurological examination
- number and type of concomitant medications
- number of clinically significant changes in vital signs (blood pressure, heart rate, respiratory rate, body temperature), body mass (weight, height).
- number of clinically significant changes in brain MRI
- number of clinically significant changes in electrocardiogram (EKG)
- number of clinically significant changes in analytical haematology, biochemistry, coagulation, serology and urine test strip results.

The primary efficacy endpoint is the average maximal increment ($M\Delta$) of anti-A β 40 antibody signal (OD in ELISA) in each subject with regard to the pre-treatment visit (either V0 or V1).

For the primary efficacy analysis, the trial will be considered successfully confirmatory regarding efficacy (immunogenicity) of ABvac40 if the average maximal increment ($M\Delta$) of anti-A β 40 antibody signal (OD in ELISA) in the verum group is >0 OD than the average $M\Delta$ in the placebo group. For the secondary efficacy analysis, the trial will be considered satisfactory if the difference of the average maximal increment ($M\Delta$) of anti-A β 40 antibody signal (OD in ELISA) in the treated group is > 1.778 OD than the average $M\Delta$ in the placebo

group; the difference that was reached between both groups in the phase I clinical trial of ABvac40.

Additionally, the following secondary efficacy endpoints will be evaluated including:

- Characterization of the immune response:
 - o Levels of anti-KLH and anti-A β 42 antibodies in plasma
 - o Level of anti-A β 40 antibodies in CSF

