8.2.5 EKG

An electrocardiogram (EKG) will be performed at visits V0, V16, V21, V23 and V25 during Part A and at visits V16B, V21B and V22B during Part B (and PDV, if applicable). All EKGs, will be assessed centrally by the Medical Advisor. Any new finding or worsening of a previous finding will be recorded in the subject's eCRF as an AE.

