9.1.3.2 Secondary Safety Analysis

The safety and tolerability analysis will be based on the safety population, comprising all subjects who took at least one dose of study medication.

Withdrawal criteria (discontinuation decision):

Withdrawal criteria will be summarized using descriptive statistics.

Number of withdrawn patients due to adverse events (AEs); reason for withdrawal:

The number and percentage of patients (in each treatment group) prematurely discontinuing study treatment due to an AE will be tabulated by SOC and PT. Listings of patients with AEs leading to discontinuation and individual narrative summaries for these cases will be provided.

Serious adverse events (SAEs)

The number and percentage of patients in each treatment group reporting at least 1 occurrence of a SAE for each unique SOC and PT will be tabulated. SAEs will be also tabulated by the relationship to study medication in treatment groups as assessed by the investigator. Listings of patients with SAEs (and deaths) and individual narrative summaries for these cases will be provided.

Physical and neurological examination

Physical findings (normal and abnormal) will be listed for each clinical trial subject. Any clinically significant abnormality developed by individual during the clinical trial and not already present at baseline will be reported as an AE.

Physical and neurological examination data will be summarized in tables.

Concomitant medication

Concomitant medication and concomitant therapy will be summarized as number of patients being treated with each type of medication/therapy classified according to ATC level 3 and World Health Organization (WHO) Drug Dictionary preferred term.

Vital signs and anthropometric data

Vital signs (blood pressure, heart rate, respiratory rate and body temperature) and anthropometric data (body mass index, weight and height) will be summarized together with changes from baseline.

Brain MRI

Brain MRI findings will be listed for each clinical trial subject and summarized in tables.

ECG

Overall interpretation of ECG results (i.e. normal or abnormal and clinical significance) as well as ECG findings will be summarized in tables.

Laboratory safety assessments

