4.1.2 Secondary Safety Variables

- Withdrawal criteria (study continuation decision)
- Physical examination:

Complete physical examinations will be performed at all face-to-face visits. These assessments include examination of the neck (including thyroid), eyes, ears, throat, abdomen, skin/mucous membranes, and cardiovascular, respiratory, genito-urinary, and musculoskeletal systems.

- Neurological examination:
Neurological examinations are performed at all face-to-face visits. These assessments include cortical function, cranial nerves, motor function, reflexes, sensory function, gait, and posture.

- Concomitant medication
Each medication will be coded to Anatomical Therapeutic Chemical (ATC) classification codes using the World Health Organization Drug classification Dictionary (WHO-DD), version WhoDrug B2 2017Q3 and defined as either a prior or concomitant medication, depending on the start and end dates of the medication, relative to the date of first dose of study treatment.

Prior medications will be defined as any medication ended prior to the first dose of study treatment.

Concomitant medications will be defined as any medication started on or after the start of study treatment or any medication taken prior to the start of study treatment and continued after the start of study treatment.

- Vital signs:
The following vital signs parameters will be monitored: blood pressure, heart rate, respiratory rate, body temperature).

- Electrocardiogram (ECG):
The following ECG parameters will be recorded: HR, PR interval, QRS and QT.

- Laboratory Assessments:
Laboratory assessments will be performed for the following: Hematology, Toxicology (reactive protein), Biochemistry, Coagulation, Serology and Urine sampling. Appendix 9.3 provides a list of that laboratory test parameters that will be recorded.

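### The numeric ECG summary reports QT without heart-rate correction although heart rate is recorded, so a rate change could mimic or mask a QT change

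*SAP*

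**What the plan says.** SAP section 4.1.2 lists what is collected: "The following ECG parameters will be recorded: HR, PR interval, QRS and QT". SAP section 7.3.6 plans descriptive statistics for the same four quantities: "ECG parameters HR, PR interval, QRS and QT will be summarized by study visit and treatment sequence group". It plans no change from baseline for these numeric values, whereas SAP sections 7.3.5 (vital signs) and 7.3.7 (laboratory) do.

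SAP section 7.3.6 then takes the normal or abnormal label already attached to each parameter and combines the labels into one category per visit. The rule for the adverse category is "Abnormal – if any one of the individual ECG parameters are abnormal at that visit". That category feeds a shift table, and all ECG results are listed.

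The protocol asks for less numeric detail. Section 9.1.3.2 says: "Overall interpretation of ECG results (i.e. normal or abnormal and clinical significance) as well as ECG findings will be summarized in tables". Section 4.1.1 counts clinically significant ECG changes among the secondary safety endpoints. Section 8.2.5 adds a central read: "All EKGs, will be assessed centrally by the Medical Advisor". The synopsis and section 8.2 exempt V22B from that read.

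No section of either document names a corrected QT, a correction formula or a corrected-QT limit.

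**The concern.** QT depends on heart rate, so a raw QT value carries two pieces of information that a safety reader needs to keep apart: how fast the heart was beating and how long repolarisation took at that rate. A table of raw QT by visit cannot separate them. If mean heart rate drifts between visits, or moves in one arm only, raw QT moves with it when nothing has happened to repolarisation. If both change, they can offset each other.

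Heart rate and QT are on the same ECG record, so the information needed to separate them is already collected. What is at stake is how far one descriptive secondary safety table can be interpreted. No test, success criterion or stopping rule uses mean QT.

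**Working it through.** The plan states no figure on this point, so there is nothing to reproduce. The check is a search of both documents followed by an illustration.

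**Search.** The ECG material is in SAP sections 4.1.2 and 7.3.6, and in protocol sections 4.1.1, 8.2, 8.2.5, 9.1.3.2 and 9.1.5.1 (the last mentions only key EKG parameters for the DSMB). None of them corrects QT for rate.

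**Inputs for the illustration.** All are assumptions, because the documents give no QT or heart-rate values: corrected QT of 400, 420 or 440 ms, and resting rates from 60 to 80 bpm.

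**Formulas.** With HR in bpm, raw QT implied by a given corrected QT is:
- Fridericia: QT = QTc × (60/HR)^(1/3)
- Bazett: QT = QTc × (60/HR)^(1/2)

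**Mimicking a change.** Hold corrected QT at 420 ms and let the rate rise from 60 to 70 bpm.
- Fridericia: 420 × (60/70)^(1/3) = 399.0 ms, so raw QT falls by 21.0 ms.
- Bazett: 420 × (60/70)^(1/2) = 388.8 ms, a fall of 31.2 ms.

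Shortening of raw QT with corrected QT constant, over the assumed 400 to 440 ms:

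| Heart-rate change | Fridericia | Bazett |
|---|---|---|
| 60 to 65 bpm | 10.5 to 11.6 ms | 15.7 to 17.3 ms |
| 60 to 70 bpm | 20.0 to 22.0 ms | 29.7 to 32.6 ms |
| 70 to 75 bpm | 8.6 to 9.5 ms | 12.6 to 13.8 ms |
| 70 to 80 bpm | 16.5 to 18.2 ms | 23.9 to 26.3 ms |

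A fall in rate over the same interval lengthens raw QT by the same amount.

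**Masking a change.** Let Fridericia-corrected QT rise from 410 to 430 ms while the rate rises from 60 to 70 bpm. Raw QT goes from 410 × (60/60)^(1/3) = 410 ms to 430 × (60/70)^(1/3) = 408.5 ms. A 20 ms prolongation appears as a shortening of 1.5 ms.

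**Between arms.** If both arms move from 60 to 70 bpm at a constant 420 ms, each loses 21.0 ms and the arm difference is zero. If one arm moves from 60 to 65 bpm and the other stays at 60, the apparent arm difference is 11.1 ms (Fridericia) or 16.5 ms (Bazett). Distortion of the between-arm contrast therefore needs a differential rate shift.

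**The case against.** The case against giving this weight is substantial, and most of it stands as a limit on size.

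- ECG heart rate is summarised at the same visits as QT, heart rate is summarised again with change from baseline under vital signs, and all ECG results are listed. A large rate shift would be visible. This stands, but only as partial mitigation: the correction is non-linear and applies to each ECG, so separate group means of HR and QT do not give the distribution of corrected values. Otherwise the reader must compute them by hand from the listing.
- Protocol section 8.2.5 provides a central read and requires new or worsened findings to be recorded as adverse events, so individual problems can reach the primary safety analysis. This stands. However, the protocol does not say how the reader handles rate, and review of individuals does not repair a group summary.
- In randomised Part A, a rate change shared by both arms largely cancels in the comparison. This stands, and nothing in the documents points to a differential shift.
- The post-dose Part A ECGs are not timed for acute effects: week 24 is 8 weeks after the week 16 dose, and week 50 is 8 weeks after the week 42 booster. Correction does not change that.
- Table specifications are in separate documents (SAP section 1.1), and QT might be shorthand for a corrected value. Neither can be ruled out, but nothing in the two documents supports either. If a corrected value was meant, the formula should be named.

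A reader might also infer that the normal/abnormal labels and the shift table rest on raw QT. The documents do not support that. SAP section 7.3.6 takes over labels assigned earlier and does not say on which QT they were based.

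**Conclusion.** The point holds for the numeric QT summary in SAP section 7.3.6 and goes no further. As planned, that summary could mimic or mask a QT change when heart rate shifts between visits or differs between arms. The scale is about 21 ms for a rise from 60 to 70 bpm at an assumed constant QTcF of 420 ms. Across all the assumed values and both formulas, a 10 bpm change gives about 17 to 33 ms. These figures show sensitivity; they do not predict what this trial's data will show.

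Two stronger readings should be resisted. One is that the summary will mislead: that requires a rate shift, which the documents give no reason to expect. The other is that a stated safety endpoint fails: the protocol's ECG endpoint is a count of clinically significant changes, and neither that count nor any primary analysis uses mean QT. This is a cheap improvement to a descriptive table.

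**What to change.** In SAP section 4.1.2, add QTcF to the ECG variables, derived for each ECG as QT/(60/HR)^(1/3), with QT in ms and HR in bpm from the same recording. In SAP section 7.3.6, summarise QTcF values and change from baseline by scheduled visit and by the existing treatment-sequence groups, in the Safety Analysis Set. In Part A those sequences already separate the two arms, and SAP section 3.1.5 analyses safety by treatment received, so no new grouping is needed.

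If categorical limits are wanted, the sponsor should fix them in advance. The documents contain none, and this point does not depend on any particular values. Keep raw QT in the listings. It would also help to state whether the existing normal/abnormal label for QT was based on a raw or a corrected value.

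The cost is one derived variable and a short additional table. No new data, visit or procedure is required, and no primary analysis changes.
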